13.1.3 Beta-D Glucan (Fungitell) Assay

The testing approach of this ancillary study involves the serial evaluation of a patient's serum for the presence of BG. The Fungitell Assay is a commercially available kit from the Associates of Cape Cod, Inc. for the identification of BG, present in a vast majority of pathogenic fungi, in the serum of patients with IFI. This assay received FDA approval for use in adults in May of 2004 to assist in the diagnosis of most IFI (including IA). The operating characteristics of the assay have been elucidated in two separate adult cohorts and are reassuring.^{63,64} The first included adult patients with newly diagnosed AML or myelodysplastic syndrome undergoing initial induction chemotherapy and receiving fungal prophylaxis with either caspofungin or itraconazole.⁶⁴ The assay was performed in 283 patients twice a week for the duration of neutropenia resulting in sensitivity, specificity, PPV and NPV for diagnosing proven or probable IFI of 100%, 90%, 43%, and 100%, respectively. More importantly, a positive Fungitell Assay result was

identified at a median of 10 days prior to the clinical diagnosis of IFI in this cohort. The second study evaluated 95 adult patients with fever and neutropenia down to 16 years of age. Thirty-eight patients with proven, probable or possible IFI were identified. The resultant sensitivity, specificity, PPV and NPV were 97.4%, 28.6%, 55.2%, and 92.3%. The specificity reported was reduced as compared to results from the prior publication as they included possible as well as probable and proven cases of IFI. Positive Fungitell Assay results preceded clinical diagnosis of IFI by a median of 5 days.⁶³ More recently, a meta-analysis including 16 prospective and retrospective studies evaluating BG levels reported a combined sensitivity of 77% and specificity of 85%.⁶⁵

One pediatric study evaluated BG levels in children using the Fungitell Assay. This study was limited to healthy children and revealed elevated baseline levels of BG in a subset of the patients.⁶⁶ To date, the Fungitell Assay testing has never been performed prospectively in immunocompromised pediatric patients and never in a population of only HCT recipients. Even if one tried to extrapolate the previously described adult data for BG testing, the results are conflicting with some studies revealing a reassuringly high sensitivity and others with a poor sensitivity. This variation likely stems from the variation across each study for testing frequency, timing of testing, and variation in the type of immunosuppressed patients. Furthermore, the elevated baseline BG levels in the one study of healthy children suggest that a higher threshold for a positive test would be necessary in a pediatric patient population.

13.1.5 Gaps in knowledge

The Fungitell Assay has shown reassuring operating characteristics in adults. Because of the proven utility of this test in adults, guidelines from the Infectious Disease Society of America have endorsed it as adjunctive diagnostic tool to guide the clinical choice for pre-emptive antifungal therapy in neutropenic adult patients at high risk for IFI despite receiving antifungal prophylaxis. A similar approach is certainly attractive to those clinicians caring for children undergoing HCT. However, there is a paucity of data regarding the operating characteristics of the Fungitell Assay in large homogeneous cohorts of children undergoing an HCT and receiving antifungal prophylaxis. It is not reasonable or appropriate to extrapolate results from adult studies and employ a similar pre-emptive approach in children. Prospective study in children is absolutely necessary to allow clinicians to transition from the traditional empiric antifungal approach to a pre-emptive strategy. The planned COG multicenter randomized controlled trial comparing the efficacy of an azole agent to caspofungin for prophylaxis against IFI in children undergoing an HCT offers a unique and likely one-time-only opportunity to establish the utility of the Fungitell Assay in a large cohort of pediatric HCT recipients.

13.2 Specific Aims and Hypotheses

Specific Aim: To define the test characteristics of weekly Fungitell beta-D-glucan Assay testing for identifying IFI in pediatric HSCT recipients receiving antifungal prophylaxis during the post-transplant neutropenic period.

Hypothesis: The Fungitell beta-D-glucan Assay will have a sensitivity that is > 90% for identifying IFI in this population of pediatric HSCT recipients. Alternatively stated, more than 90% of patients that ultimately are diagnosed with an IFI will have at least one positive Fungitell beta-D-glucan Assay prior to the actual IFI diagnosis.

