9.2 Patient Accrual and Expected Duration of Trial

In North America, from 2006-2008, an average of 688 patients per year were transplanted at COG centers that fit the eligibility criteria for this trial (CIBMTR, personal communication). Presuming constant numbers and a 20% participation rate, this trial would accrue about 138 patients per year and require 4.5-5 years (including an estimated 6 months delay for IRB approvals) to complete the accrual of 560 eligible patients, with a maximum enrollment of 590 patients to account for up to 5% ineligible enrollments. Because we will allow institutions to choose the comparator (fluconazole or voriconazole), we anticipate a high acceptance of this trial by local physicians, and indeed, our survey of the COG Transplant Centers indicated that 89% of the centers who responded would enroll patients on this trial, with a survey response rate of 80%.

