13.4 Patient Accrual

All patients to be enrolled on ACCL1131 will be offered the chance to participate in this ancillary fungal infection screening study. Those who consent will undergo weekly Fungitell Assay testing from the time of the HCT until Day +42 or until withdrawal from the study for any reason. It is suggested that specimens be obtained on Thursdays but other days are acceptable if more convenient. For those patients discharged prior to Day +42 weekly outpatient testing will be performed when possible. Each patient will have the potential for 7 separate testing points (once a week for 7 weeks). The proposed ancillary study will concurrently enroll patients from the parent trial with a goal of enrolling 400 patients.

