13.9 Statistical Design

13.9.1 Sample Size and Estimated Event Rates:

The parent trial comparing prophylaxis with an azole (fluconazole or voriconazole) to caspofungin in newly diagnosed AML patients anticipates enrollment of at least 280 patients for each arm with a total cohort of approximately 560 patients. As noted above we anticipate enrollment of approximately 400 patients. This will result in 200 patients from each study arm. Consent for testing will be included as a part of the parent trial enrollment, thus significantly limiting the need for additional resources to complete this biomarker study.

The estimated number of probable or proven IFI events for final analyses will vary by study arm. The Fungitell beta-D-glucan Assay has the potential to identify most pathogenic fungi (with the exception of *Mucorales* species and Cryptococci) and thus a majority of the probable or proven IFIs will be considered as true events.

It is challenging to establish an estimate of the event rate for IFI in this patient population as a prospective trial of anti-fungal prophylaxis in pediatric HCT recipients has never been performed. There have been three retrospective pediatric-specific studies that have attempted to define these event rates.^{26,27,55} The cumulative incidence of IFI in these three studies ranged from 8- 13%. It should be noted that these studies varied in follow-up time, in the types of transplants included, in the antifungal prophylaxis utilized and in the definition for IFI used to define the outcome. More recently an adult randomized and double blind controlled trial compared the efficacy of fluconazole prophylaxis to that of voriconazole in HCT recipients.³ Within 180 days from transplantation, 8.1% of patients on fluconazole and 4.6% of patients on voriconazole developed a breakthrough IFI. This patient population had almost no unrelated umbilical cord blood transplant patients making it a much lower risk group for IFI than our proposed patient population.

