In the proposed parent trial included patients will be the recipients of allogeneic stem cells (bone marrow, peripheral blood stem cells, or umbilical cord blood). These HCT patients are those at high-risk for an IFI and thus the anticipated incidence rate of IFI may be higher than that reported in the above referenced adult trial. Alternatively, the proposed trial will only follow patients for 100 days from transplantation and thus later onset IFI will not be identifiable. Considering the data presented above and the proposed study parameters, the COG parent trial has conservatively estimated that the IFI incidence rate will be 7% (20 events) in the azole treatment arm and 2% (6 events) in the caspofungin study arm. Because this ancillary study plans to enroll 70% (400 patients) of the parent trial patients over a three-year period the estimated event rates for the azole and caspofungin arms are 14 and 4 respectively (table 3).

| | Total | Azole Arm | Caspofungin Arm |
|------------|-------|-----------|-----------------|
| Number | 400 | 200 | 200 |
| IFI Rate | 4.6% | 7.0% | 2.0% |
| IFI Events | 18 | 14 | 4 |

13.9.2 Sensitivity, Specificity, PPV, and NPV:

The validity of a biomarker is based on whether the study appropriately categorizes patients with and without the illness in question (sensitivity and specificity). Alternatively the validity of a test can be measured by how well the test results predict the presence or absence of the disease (PPV and NPV). Collectively, sensitivity, specificity, PPV, and NPV are often referred to as the test's operating characteristics. Each component of the operating characteristics will be calculated based first on the entire cohort. As indicated in the estimates above, the incidence of is expected to vary between the two study arms. It is well documented that variations in the incidence/prevalence of a disease will impact the operating characteristics of a diagnostic test specifically for the PPV and NPV. Therefore, each assay's sensitivity, specificity, PPV and NPV will also be calculated separately for each study arm.

The operating characteristics for the Fungitell beta-D-glucan Assay will be computed as follows:

- Outcome of all IFI defined as a single positive test for the Fungitell beta-D-glucan Assay as compared to the EORTC/MSG criteria for all proven or probable IFI.

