Sensitivity, specificity, PPV and NPV and their accompanying 95% confidence intervals will be calculated using STATA statistical software version 12.0 (College Station, TX). As noted above, these parameters will first be calculated for the entire cohort and then for each study arm separately. A patient with multiple episodes of IFI will only be included in the analyses as a single IFI. As would be expected in the setting of low incidence, we anticipate that the results will show a low PPV and high NPV. This will not be an indication that the assay is not useful. The intended goal of the assay is to identify all patients with IFI at the earliest time point. In order to identify all such patients there will need to be a tolerance for a certain number of false positive results. Thus in this clinical setting the sensitivity of these assays is the most relevant parameter assuming the number of false positive results is not excessive.

13.9.3 Receiver Operator Characteristics Curve:

In addition to understanding the operating characteristics of a diagnostic test at a single defined threshold, it is also important to understand how variations in the test's threshold can alter the test's operating characteristics. The receiver operating characteristics (ROC) curve is a useful approach to illustrate how these operating characteristics will change as the threshold changes. Therefore, a receiver-operating-characteristics (ROC) curve will be generated with a series of sensitivities and specificities derived from various cutoff values. For the Fungitell Assay cutoffs of ≥ 60 , ≥ 80 , ≥ 100 , and ≥ 120 pg/mL will be used to create the ROC. The ROC curve will be displayed graphically (sensitivity vs. 1-specificity) and evaluated numerically (c-statistic). The c-statistic (also referred to as the area under the curve (AUC)) varies from 0.5 to 1.0 and is a measure of the test's ability to discriminate between patients with and without the gold standard diagnosis.²¹ A c-statistic of 0.5 is possible by chance alone while a perfectly discriminating test will result in a c-statistic of 1.0.

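### The 18 expected IFIs cannot exclude an assay sensitivity of 90% or below, and 70%, 400 patients and three years do not fit the accrual in Section 9.2

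*Combined protocol and SAP*

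**What the plan says.** Section 13.2 gives the specific aim as defining the test characteristics of weekly assay testing. It then adds a directional hypothesis: the assay "will have a sensitivity that is > 90% for identifying IFI". The same section restates this per patient: more than 90% of those eventually diagnosed "will have at least one positive Fungitell beta-D-glucan Assay prior to the actual IFI diagnosis".

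On size, Section 13.4 describes concurrent enrollment from the parent trial "with a goal of enrolling 400 patients". Section 13.9.1 adds: "This will result in 200 patients from each study arm". It takes over the parent trial's assumption that the "IFI incidence rate will be 7% (20 events) in the azole treatment arm and 2% (6 events) in the caspofungin study arm", and Table 3 turns this into 14 and 4 events, 18 in all. It also says that the ancillary study "plans to enroll 70% (400 patients) of the parent trial patients over a three-year period".

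On analysis, Section 13.9.2 states: "Sensitivity, specificity, PPV and NPV and their accompanying 95% confidence intervals will be calculated". This is done for the whole cohort and then by arm. The section treats sensitivity as the most relevant parameter. Section 13.9 gives no power, target interval width or decision rule for the 90% threshold.

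On parent accrual, Section 9.2 says "this trial would accrue about 138 patients per year" and allows 4.5 to 5 years, including about six months for IRB approvals, to reach 560 eligible patients.

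**The concern.** A hypothesis with a numerical threshold invites a yes-or-no reading of the result. With 18 events, an estimate above 90% needs only 17 or 18 positives, and either could be written up as meeting the hypothesis while the interval still reaches well below 90%. The protocol attaches weight to the answer. Section 13.7.1 says that a negative result would reassure clinicians that antifungal therapy need not be modified, and Section 13.10 expects the result to influence routine use of the test.

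The number of events depends on the number of patients, and the sentence in 13.9.1 that fixes the ancillary size combines a share, a count and a period that do not agree with Section 9.2. If the period were taken literally, the count, and so the precision, could fall below what Table 3 shows.

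**Working it through.** **Reproducing the plan's figures.**

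- IFIs: 200 × 0.07 + 200 × 0.02 = 14 + 4 = 18, as in Table 3. (Table 3 prints a total rate of 4.6%. In fact 18/400 = 4.5%; 26/560 = 4.6% is the parent-trial figure.)
- Parent accrual: 688 × 0.20 = 137.6, or about 138 a year. 560/138 = 4.06 years, plus 0.5 = 4.56 years. 590/138 + 0.5 = 4.78 years. Both lie inside the stated 4.5 to 5 years.
- Share: 400/560 = 71%, consistent with the stated 70%.

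**Precision at 18 IFIs.** When all n are positive, the exact (Clopper-Pearson) two-sided 95% lower limit is 0.025^(1/n). For n = 18 this is 0.025^(1/18) = 0.815.

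| Positive / IFIs | Estimate | Exact 95% CI |
|---|---|---|
| 18/18 | 100% | 81.5–100% |
| 17/18 | 94.4% | 72.7–99.9% |
| 16/18 | 88.9% | 65.3–98.6% |
| 14/14 (azole arm) | 100% | 76.8–100% |
| 4/4 (caspofungin arm) | 100% | 39.8–100% |

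The choice of interval does not rescue the claim. For 18/18 the Wilson lower limit is 82.4% and the one-sided 95% exact limit is 84.7%. If true sensitivity were exactly 90%, 18/18 would still occur with probability 0.9^18 = 0.15.

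**Events needed.** The smallest n for which 0.025^(1/n) exceeds 0.90 is 36 (35 by Wilson, 29 with a one-sided 95% limit). That is twice the expected 18, or 36/400 = 9% overall incidence against 4.5%. The whole parent trial expects only 20 + 6 = 26 IFIs, and 26/26 gives 86.8%. A generous count uses the Day 100 rates in Section 9.3.4: 200 × 0.12 + 200 × 0.05 = 34, although assay sampling stops at Day +42. Then 34/34 gives 89.7% two-sided and 91.6% one-sided.

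Those are best cases. For 80% power against 90% (exact, one-sided 0.025), assumed true sensitivities of 95%, 97%, 98% and 99% need about 231, 100, 70 and 54 IFIs.

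**Accrual.**

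- Parent patients in three years: 3 × 138 = 414.
- Uptake needed for 400: 400/414 = 97%.
- If the six-month start-up falls inside the three years: 2.5 × 138 = 345 parent patients, and 400/345 = 116%, which is impossible.
- At 70% uptake over three active years: 414 × 0.70 = 290 patients and 290 × 0.045 = 13 IFIs. 13/13 has an exact lower limit of 75.3%.
- Time to reach 400 at 70% uptake: 400/(138 × 0.70) = 4.1 years of active accrual.

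**The case against.** The aim is exploratory (objective 1.2.6) and optional. It is already framed as defining test characteristics, and 95% intervals must accompany every estimate. No formal test or success rule is stated, so nothing in the plan says that the hypothesis will be declared met on a point estimate. The reported intervals would show the imprecision. Assay results are withheld from treating physicians, so no trial patient's care depends on them. The event rate is described as conservative, so more than 18 IFIs may occur. All of this stands and keeps the matter minor. It does not remove the 90% hypothesis, which has no stated precision behind it.

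Two stronger readings are tempting, and the documents do not support them.

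- A reader might infer that no result could be compatible with the hypothesis. In fact 17/18 or 18/18 would agree with it; neither would exclude 90% or less.
- A reader might infer that the trial's accrual supplies only about 290 patients in three years, so that 400 cannot be reached. Section 9.2 supplies 414 parent patients in three active years. The figure of 290 requires 70% to be the uptake in those years, whereas 70% also fits 400 as a share of the final 560. No consent rate is stated as such. Section 13.4 offers the study to every parent patient with no three-year limit, so 400 is reachable over full accrual. No section says that sampling stops at three years.

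**Conclusion.** The point holds in two limited parts.

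First, at the expected 18 IFIs the planned 95% interval cannot exclude sensitivity of 90% or below whatever the data show. The best possible lower limit is 81.5%, about 8.5 percentage points short, and about twice the expected events, all positive, would be needed. This assumes roughly 18 IFIs and an exact two-sided interval; Section 13.9.2 names no interval method, but the Wilson and one-sided alternatives lead to the same conclusion at 18.

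Second, the share, count and period in Section 13.9.1 do not fit together under Section 9.2 without about 97% uptake of an optional study, and cannot be met at all if the start-up delay lies inside the three years. Any loss of precision to about 13 IFIs is conditional on 70% uptake and on sampling ending at three years.

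Severity is minor. The primary endpoint and the parent sample size are not affected.

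**What to change.** In Section 13.2, replace the hypothesis of sensitivity above 90% with estimation of sensitivity and its exact 95% confidence interval. State the limits expected with 18 IFIs (18/18: 81.5–100%; 17/18: 72.7–99.9%; 16/18: 65.3–98.6%). Add that the study is not sized to show sensitivity above 90%, so a point estimate above 90% will not be reported as establishing it. In Section 13.9.2, name the interval method.

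In Section 13.9.1, replace the three-year period with the full parent accrual period for 400 patients. If sampling really is meant to end at three years, restate the size as about 290 patients and 13 IFIs at 70% uptake, with a best-case lower limit of 75.3%.

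The cost is protocol wording and a more modest stated claim. No extra patients or samples are needed.

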13.3 Study Design

This ancillary study is a prospective observational cohort study for defining the operating characteristics of the Fungitell Assay in children enrolled on ACCL1131.

13.4 Patient Accrual

All patients to be enrolled on ACCL1131 will be offered the chance to participate in this ancillary fungal infection screening study. Those who consent will undergo weekly Fungitell Assay testing from the time of the HCT until Day +42 or until withdrawal from the study for any reason. It is suggested that specimens be obtained on Thursdays but other days are acceptable if more convenient. For those patients discharged prior to Day +42 weekly outpatient testing will be performed when possible. Each patient will have the potential for 7 separate testing points (once a week for 7 weeks). The proposed ancillary study will concurrently enroll patients from the parent trial with a goal of enrolling 400 patients.

13.5 Sample Collection and Testing Procedures (For Consenting Patients Only)

13.5.1 Sample:

In order to perform the Fungitell[®] beta-D-glucan Assay 5 mL of whole blood will be collected in a gold top serum-separator tube and labeled with the site number, COG ID number, and date (labels will be provided with the sample shipping kit). Although the above volume of blood testing will likely represent a small fraction of the blood testing performed on a HCT recipient during the period of 1 week, it may result in an important increase in certain patients (e.g., smaller children or anemic children). Therefore, we have set the following maximum limits per kilogram for blood draws related to this ancillary study: 3 mL of blood/kg body weight in an 8-week period.

13.5.2 Specimen processing:

Each specimen should be processed as follows prior to shipping:

1. Allow the blood to clot for 30-60 minutes at room temperature
2. Centrifuge the specimen for 15 minutes at 1,000 – 1,300 x g.
3. Remove the serum from the clot and place it into the provided polypropylene storage tube and label the tube.
4. A total minimum volume of 1.8 mL of serum is required to run the Fungitell[®] beta-D-glucan Assay.

13.5.3 Storing specimens:

1. Specimens should be frozen at -70°C the day of collection after following the above processing steps.
2. Specimens can be stored at -70°C until shipment. Specimens stored at -70°C may be stored indefinitely.

13.5.4 Shipping of specimens:

Each center will be provided with specimen collection kits that will be shipped to the center after patient enrollment. These kits will contain specimen collection tubes, Styrofoam lined boxes, sealing tape, labels, the ACCL1131 Fungitell[®] beta-D-glucan Assay Requisition form and a gel pack. The boxes can hold multiple frozen serum specimens. In order to optimize efficiency, specimens should not be sent until 10 specimens have been collected or every 6 months whichever comes first. As soon as a patient is enrolled, please email [name], at the Children's Hospital of Philadelphia ([contact]) to order a specimen collection kit. The shipping kit will be shipped by two-day courier. Kit requests placed on the weekend will be shipped the following Monday.

Requisitions:

Complete an ACCL1131 Fungitell[®] beta-D-glucan Assay Requisition Form for each specimen sent for testing. All areas of the requisition form must be completed to assure accurate result reporting.

Packaging:

1. Assure all specimen labels and packaging labels are correct and legible. Please use the labels provided in the kits as they are designed to withstand specimen freezing and thawing without disruption of the written patient identification information. A Sharpie marker is most effective for writing on these labels and should be used to avoid smudging of labels.
2. Place the labeled vials containing the patient serum into a biohazard plastic bag along with absorbent material such as gauze or paper towel and seal. Use the biohazard plastic bags provided in the kit.
3. Ship specimens in the boxes provided along with the frozen gel pack that should be frozen.
4. Open the box and remove the Styrofoam liner lid.
5. Place the frozen cold pack into the liner. The frozen cold pack will ensure specimen integrity during overnight shipment.
6. Place the biohazard plastic bag containing the requisition forms and specimens directly on top of the frozen cold pack.
7. Replace the Styrofoam liner lid.
8. Add the completed ACCL1131 Fungitell[®] beta-D-glucan Assay Requisition Form for each specimen and place on top of the Styrofoam liner before sealing the box.
9. Wet the sealing tape provided in the kit and seal the cardboard box.
10. Affix the UN3373 “Biological Substance Category B” label to a vertical side of the box.
11. If the specimen tube labels and requisition forms do not match when received at the testing site the specimens will not be considered valid and testing will not be performed.

Shipping Instructions:

The courier account information can be found on the ACCL1131 Fungitell[®] beta-D-glucan Assay Requisition Form provided with the shipping kit.

1. Refer to UPS website
http://www.ups.com/content/us/en/resources/ship/hazardous/biological_substances.html
to learn the current guidelines, in accordance with IATA (International Air Transport Association) for the shipping and Packaging Requirements of human body fluids.
2. Affix the UPS label to the top of the box. (The UPS label will be included in the shipping kit.) Take care not to cover any of the UN markings.
3. If your institution has a mailroom that uses UPS, take the package to the pickup area.
4. Ship packages to the following address:

UT Health Science Center at Houston
Attention: [name]
[name]
[name]
[contact]

5. Do not ship on a Friday, Saturday, or the day before a holiday.

13.5.5 Testing of specimens:

1. Testing of serum specimens for this study will be performed in batches.
 - a. Negative results are final.
 - b. Positive results are retested on the next work-day for confirmation. If original test is performed on Friday, repeat testing of positive specimens will be performed the following Monday.
2. Testing will not occur under the following conditions:
 - a. The specimen stored under unacceptable storage times and/or temperatures.
 - b. The specimen has been shipped under unacceptable time and/or temperature conditions

- c. The specimen volume is less than needed to complete the testing process.
 - d. The specimen cannot be pipetted due to viscosity.
 - e. The specimen is hemolyzed or icteric
 - f. The specimen is of a type other than serum separated off the clot.
3. If a specimen is received and falls under one of the five criteria listed above, a call will be made to the study site to inform them that testing on the specimen could not be performed.
 4. Fungitell® beta-D glucan Assay results are reported as pg/mL.

13.5.7 Laboratory of Mycology Research key personnel:

Technical Assistance:

[name]

[contact]

[contact]

Director: [name], [contact]

Testing will be performed by technicians blinded to each patient's clinical information. **Test results will not be made available to treating physicians since the utility of these tests is not yet established in children and because we will not be conducting testing in real time. Thus, results will not be utilized for clinical decision-making.**

To our knowledge BG testing is not routinely performed at many pediatric centers but may be performed at some of the COG sites. Regardless of the number of institutions offering such BG testing, we anticipate that such testing will be ordered by a subset of treating physicians. The local BG results will not be included in our final analysis of the biomarker assay's operating characteristics. However, these results may effect a change from fungal prophylaxis to preemptive or empiric therapy and may encourage or discourage more comprehensive efforts to diagnose a proven or probable IFI in any given patient. This in turn may falsely influence our evaluation of the Fungitell beta-D-glucan Assay's operating characteristics. For each patient we will identify whether local BG testing has been performed and, via a sensitivity analysis, explore whether such a practice influences the operating characteristics. The plans for this sensitivity analysis are described in more detail in Section 13.9.4 below.

The Fungitell beta-D-glucan Assay is reported in pg/ mL of patient's serum. The manufacturer recommendation for a single positive Fungitell Assay result of > 80 pg/mL will be used to define a positive test.

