7.1.1 History, Demographic and Clinical Information

Demographic and clinical information collected at baseline will include age, sex, performance status, Down syndrome, ethnicity, height, weight, and episodes of fully-treated proven/probable yeast infection in the 3 months prior and receipt of systemic antifungal therapy within 7 days prior to enrollment. Other information collected will include type of malignancy or underlying diagnosis, relapse status, donor type, degree of donor match, stem cell source, conditioning regimen and graft-versus-host disease (GVHD) prophylaxis.

7.2 **Optional Studies**

7.2.1 (1→3) Beta-D Glucan Assays

If patient consent is obtained, Fungitell beta-D-glucan Assay will be performed during the period of neutropenia in order to identify IFI. 5 mL of whole blood will be collected in a gold top serum-separator tube once weekly. See Section 13 for sample collection, processing and shipping details.

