14.1.1 Sample Collection

Collect 5 mL of peripheral blood in a purple top (EDTA) tube at study entry and at end of study (Day +100 +/- 7 days), optimally when the patient has an ANC >1000/ μ L. Patients with weights less than 20 kg may have only 3 mL collected. Specimens may be shipped fresh to the BPC, where the plasma and buffy coat will be stored at -20°C.

14.1.2 Labeling:

Label the tubes with the patient's BPC #, specimen type, and date of collection.

14.1.3 Shipping:

Ship sample at room temperature by FedEx priority overnight delivery. Shipping labels can be obtained via the Biopathology Center's Kit Management application. Blood may be shipped Monday through Friday for receipt on Tuesday through Saturday. Include a COG Specimen Transmittal Form with each shipment.

The SNP sample should be shipped to:

COG Biopathology Center – ACCL1131
Nationwide Children's Hospital
[name]*
[name]
[contact]
[contact]

*Be sure to include the room number. Packages received without the room number may be returned to the sender.

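### In the optional beta-D-glucan sub-study, seven weekly 5 mL draws exceed the protocol's own 3 mL/kg limit for a child under 11.7 kg who takes all seven, and no rule says how to comply

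*Combined protocol and SAP*

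**What the plan says.** Section 7.2.1 sets the volume and frequency for consenting patients: "5 mL of whole blood will be collected in a gold top serum-separator tube once weekly". Section 13.5.1 gives the same volume: "5 mL of whole blood will be collected in a gold top serum-separator tube and labeled".

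Section 13.4 offers the sub-study to every enrolled patient and describes "weekly Fungitell Assay testing from the time of the HCT until Day +42 or until withdrawal from the study for any reason". It then states: "Each patient will have the potential for 7 separate testing points (once a week for 7 weeks". The three therapy delivery maps (Sections 4.2.2, 4.2.4 and 4.3.1) mark the assay on map Days 1, 8, 15, 22, 29, 36 and 43, where map Day 43 is HCT Day +42.

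Section 13.5.1 acknowledges that "it may result in an important increase in certain patients (e.g., smaller children or anemic children", and for that reason limits blood for this sub-study to "3 mL of blood/kg body weight in an 8-week period". It gives no reduced volume, no permitted number of draws by weight, and no rule on which weeks to keep. Section 13.5.2 requires at least 1.8 mL of serum, and Section 13.5.5 says that specimens with too little volume are not tested.

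The other optional sample, for SNP genotyping, is scaled to weight in Sections 7.2.2 and 14.1.1: "Patients with weights less than 20 kg may have only 3 mL collected". Section 3.2.1 sets the lower age limit at 3 months for fluconazole centers and 2 years for voriconazole centers.

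**The concern.** The fixed volume, the weekly schedule and the limit cannot all be met in a small child who follows the full schedule. The site must either exceed a limit set to protect that child or stop drawing part-way through the period at risk.

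Stopping early matters for the sub-study's main quantity. Section 13.2 hypothesizes sensitivity above 90%, meaning at least one positive test before the IFI is diagnosed. A child whose sampling ended in week 3 and who is diagnosed in week 5 has had fewer chances of a positive result. If the earlier tests were negative, that child counts as a miss, although no test was taken near the diagnosis. The two sensitivity analyses in Section 13.9.4 deal with locally ordered testing and false-positive factors. Neither deals with sampling cut short by the limit.

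**Working it through.** **Inputs.** Volume per draw: 5 mL (7.2.1, 13.5.1). Maximum draws: 7 (13.4). Limit: 3 mL/kg in 8 weeks (13.5.1). Minimum serum: 1.8 mL (13.5.2). Expected IFIs in the sub-study: 18 among 400 patients (13.9.1, Table 3).

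**Number of draws.** The delivery maps mark seven assay days, which reproduces the seven in Section 13.4. From map Day 1 to map Day 43 is 42 days, so all seven fall inside the 8-week window.

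**Threshold weight.** Total volume = 7 × 5 = 35 mL. Lowest weight at which it fits = 35 / 3 = 11.67 kg. For fewer draws the threshold is 5k/3:

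| Draws taken (k) | Volume (mL) | Lowest weight that fits (kg) |
|---|---|---|
| 7 | 35 | 11.7 |
| 6 | 30 | 10.0 |
| 5 | 25 | 8.3 |
| 4 | 20 | 6.7 |

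**Full draws allowed at a given weight.** Number = 3 × weight / 5, rounded down, to a maximum of 7. The last draw assumes weekly sampling from map Day 1.

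| Weight (kg) | Limit (mL) | Full 5 mL draws | Last draw (map day) | Excess if all seven taken (mL) |
|---|---|---|---|---|
| 6 | 18 | 3 | 15 | 17 |
| 8 | 24 | 4 | 22 | 11 |
| 10 | 30 | 6 | 36 | 5 |

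At 6 kg, all seven draws come to 35/6 = 5.8 mL/kg, or 35/18 = 1.9 times the limit.

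**Could smaller draws solve it?** Only in part. The documents give no serum yield, so I assume a range of 40% to 60% of blood volume. The blood needed for 1.8 mL of serum is 1.8/yield, and seven such draws fit from 7 × (1.8/yield)/3:

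| Assumed yield | Blood per draw (mL) | Lowest weight for seven draws (kg) |
|---|---|---|
| 40% | 4.5 | 10.5 |
| 50% | 3.6 | 8.4 |
| 60% | 3.0 | 7.0 |

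At 5 kg the limit allows 15/7 = 2.14 mL per weekly draw, which would need a yield of 1.8/2.14 = 84%. For the smallest infants, some draws have to be dropped.

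**Leverage on the estimate.** With 18 expected IFIs, two misses caused by truncated sampling would give 16/18 = 88.9%, below the hypothesized 90% even if the assay detected every other case. This illustrates how few misses matter. It does not predict that two will occur.

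**The case against.** The strongest reply is that a maximum is meant to truncate. Section 13.5.1 foresees the small child and sets a ceiling, and Section 13.4 speaks only of a potential for seven tests. After discharge, "For those patients discharged prior to Day +42 weekly outpatient testing will be performed when possible", and Section 7.2.1 places testing in the neutropenic period, so many children may have fewer than seven draws. This stands in part: the 11.7 kg figure holds only for a child who takes all seven, and an over-draw would be a departure from the limit. It does not supply the missing rule. The text neither scales the volume nor says which draws to give up.

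Four stronger readings are tempting, and the documents do not support them.

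- *Sites are told to draw weekly with no route to the limit.* The delivery maps, the footnote to the 7.1 table and Section 7.2.1 all refer to Section 13, where the limit stands beside the 5 mL volume. A site that follows the reference will find it.
- *Infections go undetected.* Section 13.5 withholds assay results from treating physicians, and blinded committee review of clinical material classifies IFIs. Missing draws lose chances of an assay positive and nothing more.
- *The SNP blood counts too.* The limit covers draws for this sub-study only. The SNP sample is a separate optional study under Section 14.
- *Permitted draws should be spread over Day 0 to +42.* That would work against the aim of evaluating weekly testing and against the analysis in Section 13.9.3 that requires two consecutive positives.

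**Conclusion.** The conflict is real and the arithmetic is exact. At 5 mL per draw, the full seven-draw schedule exceeds the limit for a child under 11.7 kg; with six, five or four draws the threshold falls to 10.0, 8.3 or 6.7 kg. Within the limit and drawing weekly from the start, sampling ends after three draws at 6 kg, four at 8 kg and six at 10 kg.

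The consequence is confined to an optional, exploratory aim. Truncated sampling could bias the sensitivity estimate downward, provided such patients stay in the analysis and their earlier tests were negative. The effect cannot be sized, because the documents give no weight distribution. That some eligible infants and toddlers weigh less than 11.7 kg is an assumption, but a safe one given entry from 3 months. They are probably concentrated at fluconazole centers, since voriconazole centers enroll only from 2 years.

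The matter should be corrected because the limit was written for exactly these children and the correction is cheap. Which volume or limit is appropriate is for the sponsor to decide.

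**What to change.** Reconcile Sections 7.2.1, 13.4, 13.5.1 and the three delivery maps so that the schedule complies with the stated limit:

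1. Add a weight-band table to Section 13.5.1 giving the draw volume and permitted number of draws, consistent with the 1.8 mL serum minimum. The sponsor should choose which weeks to keep, weighing the weekly-testing aim and the consecutive-positives analysis.
2. Repeat the limit in the 7.1 table and on the three delivery maps.
3. Restrict the statement of seven testing points in Section 13.4 to children for whom seven draws fit.
4. Add to Section 13.9.4 a sensitivity analysis that excludes patients whose sampling was cut short by the limit.

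The cost is one small table, some wording and one extra analysis. The downside is fewer or smaller samples from the youngest participants in an optional study.
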